- a) Direct blow to the head, face, neck or a blow elsewhere on the body with an “impulsive” force transmitted to the head.
- b) Rapid onset of short-lived impairment of neurologic function in one or more of the following clinical domains that resolves spontaneously:
 - 1. symptoms: somatic (eg, headache), cognitive (eg, feeling like in a fog) and/or emotional symptoms (eg, lability).
 - 2. physical signs (eg, loss of consciousness, amnesia).
 - 3. behavioural changes (eg, irritability).
 - 4. cognitive impairment (eg, slowed reaction times).
 - 5. sleep disturbance (eg, drowsiness).
- c) No abnormality on standard structural neuroimaging studies, if such neuroimaging studies are completed for a clinically-indicated reason. Note: neuroimaging is not a part of this study protocol. Study participants will not undergo neuroimaging as part of this study.

Subjects will be randomized in a 1:1 fashion. DHA is an omega-3 fatty acid that occurs naturally in fish oil and algae. There are many dietary supplements containing DHA available in the marketplace. Martek Biosciences provides an algae-based DHA compound which minimizes the side effects of “fishiness” in both flavor and “fish burps.” The DHA produced by Martek Biosciences is also used for many infant formula companies in the US. DHA and identical placebo will be provided by Martek Biosciences.

The DHASCO capsules are supplied as 950 mg capsules with an effective dose of 500 mg DHA per capsule. The placebo capsules are supplied as 950 mg capsules consisting of 475 mg corn oil and 475 mg soy oil. Both DHA and placebo are flavored with sweet orange flavoring and masking agents.

They are supplied in sealed white plastic bottles containing 100-200 capsules per bottle, depending on dose. Each bottle has the lot number stamped on it. The capsules will be stored in a dry, locked compartment at room temperature (60 to 75 F). Martek's Quality Assurance department completes regularly scheduled chemical and long-term stability analyses on each lot of capsules. If shipments will occur during warmer months, arrangements will be made for capsules to be shipped with ice packs or other temporary refrigeration. Capsules will be dispensed to subjects in separate bottles in quantities sufficient to last until their next appointment. Any unused capsules will be returned to the PI or research staff and sent to the pharmacy for destruction in compliance with Children's regulations.

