The primary outcomes of this feasibility trial are to determine the willingness of patients to be randomized, the expected rate of enrollment based on the clinic population, and protocol adherence of enrolled study participants. We anticipate the results from this study will provide data to inform a larger randomized trial of DHA for the treatment of pediatric sports concussion. Secondary outcomes are time to clearance to return to play (in days) and improvement in balance, as assessed by the Balance Error Scoring System (BESS) which is a component of the Sport Concussion Assessment Tool 3 (SCAT-3). Time to clearance to return to play was chosen as a clinically significant measurement for medical professionals in the sports medicine field. The investigators will determine clearance for return to full competitive game play (Stage 6 of graduated return to play protocol) according to Consensus Statement guidelines and following the law in Texas, House Bill 2038. Criteria for return to play include complete clinical recovery from the concussion including returning to baseline symptoms, exam and

neurocognitive function and successful completion of a gradual return to play progression. The BESS was chosen because it is a relatively simple assessment that has been noted by the investigators to be a good predictor of neurological recovery.

In addition to time to return to play and the BESS, the SCAT-3 and Immediate Post Concussion Assessment and Cognitive Testing (ImPACT) computerized neurocognitive testing programs will be used to evaluate recovery. The SCAT-3 is a standardized method of evaluating injured athletes for concussion and can be used in athletes aged from 10 years and older. The ImPACT program is a computerized exam that helps to quantify the degree of symptom, injury, or dysfunction that occurs after a sports related concussion. Although this test is utilized by many professionals, college, and high school sports programs throughout the country, it is unclear if its use contributes to a safer or more expedited return to activity.

Finally, information on side effects will be collected at every visit in order to track the rate and severity of side effects in this patient population.

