At Visit 1, the patient will sign the consent form and complete the SCAT-3, ImPACT, and concussion assessment questionnaire. The ImPACT computerized test has standardized scores for subjects in the age range for the population and is used clinically to assess neurocognitive deficits after sports concussion. The concussion assessment consists of medical history, symptom assessment, and sports and school activity components. Subjects will be randomized to either DHA or placebo in a 1:1 ratio, and receive enough DHA or placebo capsules to reach the target dose of 2 g of DHA per day (or placebo) until the day of their next appointment. Subjects will be instructed to take 2 capsules at breakfast and 2 capsules at dinner (with food). Subjects will take their first dose in the office to assure their ability to swallow the pills. Subjects will be instructed to bring their pill bottle with any remaining pills with them to their next research visit. This visit will last approximately 90 minutes.

Visit 2 will occur 7 days after enrollment (+/- 2 days). Subjects will complete the SCAT-3 and ImPACT at this visit. Subjects will also be asked if they are experiencing any side effects. At this visit, the research personnel will count how many capsules remain in the bottle, and enough additional capsules will be dispensed to last a week, until the next scheduled visit. This visit will last approximately 90 minutes.

Visit 3 will occur at 2 weeks after enrollment (+/- 2 days). Subjects will again undergo the SCAT-3 and ImPACT, and be asked about side effects. The research personnel will count the capsules returned and the patient will receive enough capsules for another 2 weeks, until their next appointment. This visit will last approximately 90 minutes.

Visit 4 will occur at 4 weeks after enrollment (+/- 2 days). Subjects will complete the SCAT-3 and ImPACT at this visit, and be asked if they are experiencing any side effects. The research personnel will count the capsules returned and the patient will receive enough capsules for another 8 weeks, until their next appointment. This visit will last approximately 90 minutes.

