In addition, subjects who are released to play prior to Visit 4 (4 weeks post-enrollment) will not be asked to return for additional weekly visits, but instead will be asked to complete a symptom questionnaire and answer questions about side effects online via MyChart in lieu of these visits. Once patients have returned to their baseline and are returned to play, there is no need for additional visits for well subjects. As a safety precaution, subjects will fill out symptom questionnaires and a side effects scale so that if a patient does worsen, additional clinical follow-up may be scheduled. This does not place the patient at additional risk, and encourages protocol compliance as subjects will not be required to miss additional school or other activities for appointments that are not clinically necessary. Subjects will receive follow-up phone calls to remind them to complete these forms online. Subjects will still be asked to return for visit 5, but will not be charged for this visit if it is not clinically indicated.

5. Criteria for Inclusion of Subjects:

1. Male or females age 14-18 inclusive
2. Diagnosed with concussion due to sports-related injury. Concussion is defined as:
 - a) Direct blow to the head, face, neck or a blow elsewhere on the body with an “impulsive” force transmitted to the head.
 - b) Rapid onset of short-lived impairment of neurologic function in one or more of the following clinical domains that resolves spontaneously:
 - i. Symptoms: somatic (eg, headache), cognitive (eg, feeling like in a fog and/or emotional symptoms (eg, lability).
 - ii. Physical signs (eg, loss of consciousness, amnesia).
 - iii. Behavioral changes (eg, irritability).
 - iv. Cognitive impairment (eg, slowed reaction times).
 - v. Sleep disturbance (eg, drowsiness).
 - c) No abnormality on standard structural neuroimaging studies, if such neuroimaging studies are completed for a clinically-indicated reason. Note: neuroimaging is not a part of this study protocol. Study participants will not undergo neuroimaging as part of this study.
3. Concussion within 4 days of enrollment
4. Presenting for treatment to the Sports Medicine Center at Children's Medical Center

6. Criteria for Exclusion of Subjects:

1. Subjects not actively participating in an organized sport at time of enrollment
2. Subjects who received a concussion from an event other than playing a sport (motor vehicle accident, fall, etc.)

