Burping or fishy after-taste have been infrequently reported. In clinical studies with DHASCO, these mild gastrointestinal side effects may be reduced by taking capsules with food. Other mild gastrointestinal symptoms such as diarrhea have been reported infrequently, but the incidence of these AEs is not different from that observed in subjects receiving placebo. DHA supplementation may result in modest elevations of LDL-C and non-HDL-C in some individuals. However, the increased level of LDL-C was associated with a shift of lipoprotein particle size toward larger, less atherogenic subfractions. In summary, adverse event monitoring revealed an excellent safety and tolerability profile for DHASCO.

There are no known serious side effects from taking DHA. However, based on the experiences of 379 men and women, both children and adults, the following side effects occurred at a greater rate than in placebo and in greater than 2% of participants: burping (17.7%), headache (8.97%), bad taste in the mouth (7.65%), back pain (3.43%), abdominal distension (2.11%), and weight increase (2.11%).

Patients taking placebo may also experience side effects. These side effects occurred more frequently than DHA and in greater than 2% of participants, and are based on the experiences of 200 men and women, both children and adults, who took placebo during clinical trials of DHA: diarrhea (10%), flatulence (excessive gas; 8.5%), common cold (7%), upper respiratory infection (6%), upset stomach

(4%), nausea (3.5%), rash (3.5%), increased blood triglycerides (3%), frequent bowel movements (2.5%), cough (2.5%), stomach flu (2%), influenza (2%), and contact dermatitis (2%).

10. Subject Safety and Data Monitoring:

All patients will receive standard clinical treatment for concussion. Participation in this study does not preclude additional treatment for concussion as indicated, including, but not limited to, additional medications for headache, referrals for neurological or neuropsychological consultations, or other medications or consultations as deemed clinically appropriate. Patients with no diagnostic imaging studies for the current concussion who are later referred for imaging and found to have radiographical evidence of acute traumatic brain injury may continue on the study, but will also be referred for appropriate care as necessary based on imaging (i.e., referrals to neurology, neurosurgery, etc, as clinically indicated).

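### Side effects are collected in a mode that depends on recovery, with none listed at Visit 1, week 8 or Visit 5 and no rule for counting headache

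*Combined protocol and SAP*

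**What the plan says.** All references are to the combined protocol and SAP.

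- **Purpose (Section 3, Concise Summary of Project).** The plan states that "information on side effects will be collected at every visit in order to track the rate and severity of side effects in this patient population".
- **Clinic visits (Section 4, Study Procedures).** At Visit 2, "Subjects will also be asked if they are experiencing any side effects". Visits 3 and 4 are worded similarly. No form, item list or severity grade is named, and Section 7 (Sources of Research Material) lists no side-effect form among the data sources.
- **After early release (Section 4).** The plan says that "subjects who are released to play prior to Visit 4 (4 weeks post-enrollment) will not be asked to return for additional weekly visits". Instead they "will be asked to complete a symptom questionnaire and answer questions about side effects online via MyChart in lieu of these visits". The reason given is that "subjects will fill out symptom questionnaires and a side effects scale so that if a patient does worsen", further clinical follow-up can be arranged.
- **Contacts with no listed side-effect question (Section 4).** Visit 1 lists the SCAT-3, ImPACT and a concussion questionnaire that includes a symptom assessment, then randomisation and the first dose in the office. The week-8 call covers general wellbeing, capsule supply and questions. Visit 5 lists the SCAT-3, ImPACT and a capsule count.
- **Headache.** The concussion definition in Section 3 begins with "symptoms: somatic (eg, headache), cognitive (eg, feeling like in a fog) and/or emotional symptoms (eg, lability". Section 9 (Potential Risks) lists headache at 8.97% among effects seen more often on DHA than on placebo in 379 people. It does not give the placebo rate.

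**The concern.** The switch from clinic question to online scale is triggered by release to play. That event comes after randomisation, time to it is a secondary outcome, and Section 1 hypothesises that DHA shortens it. How side effects are recorded therefore depends on something the treatment is expected to change. If a self-completed scale picks up more complaints than a spoken question, the arm that recovers faster will show more side effects for that reason alone.

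The descriptive aim is affected whether or not DHA works. An overall rate built from two modes depends on how many subjects happened to recover early, and a question without a grade does not deliver the severity that Section 3 promises.

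Headache adds a separate problem. Staff could log a headache in an unrecovered subject as a side effect or leave it out as concussion. The plan does not say which, so different staff may decide differently.

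The data go to the monitoring board (Section 10) and are meant to inform a larger trial (Section 3), so an avoidable inconsistency could be carried forward.

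**Working it through.** The plan gives no target, power or error rate for side effects, so there is no figure of its own to reproduce. Its listed percentages are consistent with whole counts: 34/379 = 8.97% and 67/379 = 17.7%.

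**1. Coverage.** The last contact with a listed side-effect enquiry is Visit 4, at week 4 of 12. That leaves 12 − 4 = 8 weeks of dosing with none listed. Subjects who stop early are asked back for Visit 5, which also lists none.

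**2. Effect of mixed modes on the overall rate.** Let p be the true rate, s the share of events each mode detects, and f the share released early.

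Observed rate = p × [s_online × f + s_clinic × (1 − f)]

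The documents give neither s nor f. Assume s_clinic = 0.5 and s_online = 0.9, and take p = 17.7%, the Section 9 figure for burping:
- f = 40%: 0.177 × (0.36 + 0.30) = 11.7%
- f = 80%: 0.177 × (0.72 + 0.10) = 14.5%

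The same true rate is thus reported 2.8 points apart depending on recovery alone. The standard error of a 13% rate in 40 subjects is √(0.13 × 0.87/40) = 5.3 points.

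**3. Effect on the arm difference.** With the same true rate in both arms:

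Artefact = p × (s_online − s_clinic) × (f_DHA − f_placebo)

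If equal shares are released early, the artefact is zero at any p. Otherwise, with the same assumed s:

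| p | Released early, DHA vs placebo | Artefact | Standard error of difference, 20 per arm | Rejection rate at nominal 5% |
|---|---|---|---|---|
| 8.97% | 70% vs 50% | 0.0897 × 0.4 × 0.2 = 0.7 points | 7.9 points | 5.1% |
| 17.7% | 70% vs 50% | 0.177 × 0.4 × 0.2 = 1.4 points | 10.7 points | 5.2% |
| 60% | 70% vs 50% | 0.6 × 0.4 × 0.2 = 4.8 points | 15.7 points | 6.1% |
| 60% | 80% vs 40% | 0.6 × 0.4 × 0.4 = 9.6 points | 15.7 points | 9.4% |

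The standard error is √(2 × p̄ × (1 − p̄)/20), where p̄ is the mean observed rate. The rejection rate is a two-sided normal approximation.

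A harsher assumption, that the question yields 10% and the scale 30%, with 60% versus 40% released early, gives:
- DHA: 0.6 × 30% + 0.4 × 10% = 22%
- Placebo: 0.4 × 30% + 0.6 × 10% = 18%

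That is a 4-point artefact against a standard error of √(2 × 0.20 × 0.80/20) = 12.6 points.

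These models put each subject wholly on one mode. A subject released after Visit 2 has already answered the clinic question, so the contrast between modes is, if anything, exaggerated.

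**4. Headache.** At 8.97%, 20 × 0.0897 = 1.8 DHA subjects are expected to report it. Suppose that every concussion headache in an unrecovered subject is logged as a side effect, that recovered subjects have none, and that DHA alone adds 8.97%. Treating 8.97% as the whole excess is generous, because the placebo rate is not given. With h the headache prevalence in unrecovered subjects:

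DHA = 1 − [1 − h(1 − f_DHA)] × (1 − 0.0897); placebo = h(1 − f_placebo)

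- h = 30%, release 50% vs 50%: 22.6% − 15.0% = +7.6 points
- h = 70%, release 70% vs 50%: 28.1% − 35.0% = −6.9 points

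The same drug effect can appear, shrink or reverse under that logging habit. If staff instead put such headaches down to concussion, drug-related ones go uncounted. The missing rule decides which applies.

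**The case against.** The case for leaving the plan alone has several parts.

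- **The form may be the same.** Section 4 describes the online enquiry both as questions about side effects and as a scale. The clinic might use the same form, and tracking severity implies more than a yes/no question. This stands in part: only the difference in mode, in person or online, is certain. A different form is what the wording suggests, but the plan does not say so. Nor does it give question wording that would show whether subjects must attribute a complaint to the capsules.
- **There is a baseline.** A reader might infer that nothing is recorded before dosing. The documents do not support that: Visit 1 includes the SCAT-3 and a symptom assessment, described before randomisation and the first dose. What is missing is a baseline on the side-effect form, and any statement that the symptom baseline will be used when side effects are counted.
- **Randomisation and blinding.** A reader might infer that the arms cannot be compared. That does not follow either. Mode depends on release, not on arm, and the artefact is zero if release is equal. Bias needs both a difference in yield between modes and a difference in release between arms, and the documents quantify neither. The two mechanisms can also pull in opposite directions, so no net direction is established.
- **Low stakes.** The Section 3 primary outcomes are willingness to be randomised, enrolment and adherence. Section 13 (Biostatistics) names no test of side effects by arm, and about 1.8 expected headaches could not support one. This stands, and it is why the point is minor. It does not answer the effect on the descriptive rate or the contacts with no listed enquiry.

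**Conclusion.** The point holds as a minor one. As written, collection mode changes with release to play; no side-effect enquiry is listed at Visit 1, the week-8 call or Visit 5, despite the promise of every visit; and no rule says how headache is counted against the Visit 1 symptom record.

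The overall rate is affected directly. The arm comparison is at risk only if release differs by arm, which the trial hypothesises but has not shown. The size is unknown. Every detection share, release share and headache prevalence used here is an assumption, and in most of these scenarios the distortion is small beside sampling error at 20 per arm. The sample size does not need to change.

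**What to change.** 1. Use the side effects scale already planned for MyChart, identified by name and with severity grades, at every contact: Visit 1 before the first office dose, Visits 2 to 5, the week-8 call and MyChart. Have subjects complete it themselves in clinic, so that the mode stays close to the online one.
2. Count an item as treatment-emergent if it is new or worse than at Visit 1, without asking the subject for the cause. For headache, use the Visit 1 symptom assessment as well.
3. Report headache and the other items by arm on that basis, descriptively.
4. Add the scale to the data sources in Section 7.

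The cost is one extra pre-dose completion, a few minutes per contact, and higher raw counts in both arms. One limit remains: a drug-related headache no worse than the subject's Visit 1 headache will still not be counted. The rule does, however, apply identically to both arms and to recovered and unrecovered subjects.
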